9.5.1.5.4 VITAL SIGNS AND WEIGHT/HEIGHT MEASUREMENTS

Vital sign measurements (ie, systolic and diastolic blood pressure [mmHg], pulse [beats per minute], temperature [in centigrade]), body weight (kg), and height (cm) will be obtained at the visits designated in the Schedule of Procedures/Assessments (Table 5) by a validated method. Blood pressure and pulse will be measured after the subject has rested.

Eisai Confidential Page 49 of 71 FINAL: 29 Jan 2021

Eisai Confidential Page 50 of 167

a: On Day 15 of each cycle, peripheral blood smear morphology assessment can be omitted at the discretion of the investigator or subinvestigator, if there was no concern for safety of the subject. If peripheral blood smear morphology assessment is confirmed to be abnormal (eg, blood cell dysplasia, appearance of blast cells) and myeloid malignancy including myelodysplastic syndrome is suspected, then conduct bone marrow aspirate with cytogenic testing (eg, G-banding).

b: Screening 2 only.

9.5.1.5.5 PHYSICAL EXAMINATIONS

Physical examinations will be performed as designated in the Schedule of Procedures/Assessments (Table 5). Documentation of the physical examination will be included in the source documentation at the site. Only changes from Screening 2 physical examination findings that meet the definition of an AE will be recorded on the CRF.

9.5.1.5.6 ELECTROCARDIOGRAMS

ECGs will be obtained as designated in the Schedule of Procedures/Assessments (Table 5) at each site. Standardized, 12-lead ECG recordings that permit all 12 leads to be displayed on a single page with an accompanying lead II rhythm strip below the customary 3×4 lead format are to be used. In addition to a rhythm strip, a minimum of 3 full complexes should be recorded from each lead simultaneously. ECGs will be obtained after the subject has rested.

ECG parameters (heart rate, PR interval, QRS interval, QRS axis, QT interval, QTcF interval, RR interval) will be recorded on the CRF. ECG findings (normal, abnormal not clinically significant, abnormal clinically significant) will also be recorded. QTc will be corrected using Fridericia method (QTcF).

An ECG abnormality may meet the criteria of an AE as described in this protocol (see Section 9.5.1.5.1). In these instances, the AE corresponding to the ECG abnormality will be recorded on the CRF.

9.5.1.5.7 OTHER SAFETY ASSESSMENTS

9.5.1.5.7.1 ECOG PS

An ECOG performance status should be done at each visit as designated in the Schedule of Procedures/Assessments (Table 5).

9.5.1.5.7.2 Pregnancy Test

An hCG or β -hCG test will be performed for women of childbearing potential at each site. A serum or urine sample will be taken at visits as designated in the Schedule of Procedures/Assessments (Table 5).

All females will be considered to be of childbearing potential unless:

- Postmenopausal (amenorrheic for at least 12 consecutive months without other known or suspected cause)
- Sterilized surgically (bilateral tubal ligation at least 1 month before dosing, total hysterectomy, or bilateral oophorectomy at least 1 month before dosing).

9.5.1.6.7.3 Viral Tests

Hepatitis B surface (HBs) antigen, HBs antibody, hepatitis B virus core (HBc) antibody, hepatitis C virus (HCV) antibody, and HIV antibody tests will be performed at Screening 2.

Eisai Confidential Page 50 of 71 FINAL: 29 Jan 2021

When subjects have HBs antibody or HBc antibody positive results, HBV-DNA tests will be performed. When subjects have HCV antibody positive results, HCV-RNA tests will be performed. Viral tests will be performed at each site.

9.5.2 Schedule of Procedures/Assessments

9.5.2.1 Schedule of Procedures/Assessments

Table 5 presents the schedule of procedures/assessments for the study.

Eisai Confidential Page 51 of 71

Table 5 Schedule of Procedures/Assessments in Study E7438-J081-206 (EZH-206)

Phase		Due tweetment			Тиол	t-mont		Falls	
rnase		Pre-treatment		Treatment				Follow-up	
Period	Screening 1	Screening 2 ^a	Baseline	Cyc	ele 1	Cycle 2	and later	Discontinuat ion	Final observation
Day		Within 28 days before admin	Within 3 days before admin	1	15 (±3)	1 (±3)	15 ^k (±3)	(+7)	30 days after last dosing (+7) ^{b, 1}
IC for EZH2 gene mutation test	X								
Archival tumor sample submission	X								
IC for study treatment ^c		X							
Demographic data	$[X]^d$	X							
Inclusion/exclusion Criteria		X	X						
Enrollment		X							
Medical history/Current medical condition		X							
Previous therapy		X							
Height		X							
Body weight		X	X		X	X	X	X	X
Physical examination		X	X		X	X	X	X	X
Vital signs		X	X		X	X	X	X	X
ECOG performance status		X	X			X		X	
12-lead ECGs		X	X		X	X	X	X	
Pregnancy test (if applicable)		X						X	
Virus test		X							
Hematology ^j		X	X		X	X	X	X	X
Blood chemistry		X	X		X	X	X	X	X
Urinalysis		X	X		X	X	X	X	X
PK blood sampling ^e					X	[X]			
Tumor assessments (CT/endoscopy) ^f		X				[3	X]	X	
Tumor assessments (PET) ^g		X				[3	X]		
Bone marrow examination (bone marrow aspiration or biopsy) ^h		X				[3	X]		
Tazemetostat administration ⁱ		Continuous 28-day cycle of twice daily (BID)							
Adverse events		From informed consent for study treatment to final observation							
Concomitant drug/therapies From informed consent for study treatment to final observation									

Eisai Confidential Page 52 of 71

Note, [X]: In case to perform.

admin = administration, BID = twice daily, C#D# = Cycle # Day #, CR = complete response, CT = computed tomography, ECG = electrocardiogram, ECOG-PS = Eastern Cooperative Oncology Group-Performance Status, IC = informed consent, PET = positron emission tomography, PK = pharmacokinetics.

- a: Screening 2 assessments may be used as baseline assessments if performed within 3 days of the first administration of study drug.
- b: When subject needs to receive other anti-tumor therapy within 30 days after the final study drug administration, final observation must be conducted before initiation of other anti-tumor therapy and the data within 7 days before next anti-tumor therapy can be used for final observation.
- c: Obtain from the patients who has confirmed tumor EZH2 gene mutation in central laboratory.
- d: Collect demography information described in Section 9.5.1.1.
- e: Blood samples for PK analyses of tazemetostat will be collected in C1D15 and C2D1 predose of first administration.
- f: The data of CT scan/endoscopy before informed consent within 28 days from study drug administration can be used as Screening 2 data if it meets the requirement of the protocol. Perform tumor assessment at Screening 2, every 8 weeks from first study drug administration for first 32 weeks (±1 week, eg, C2D21 to C3D7, C4D21 to C5D7...C8D21 to C9D7), then every 12 weeks (±1 week, eg, C11D21 to C12D7, C14D21 to C15D7...) and discontinuation. The data within 28 days can be used as discontinuation data. If gastrointestinal disease were suspected, endoscopic examination will be performed at Screening 2. If exists, perform when it is required to confirm CR as soon as possible or when clinically indicated.
- g: The data of PET scan before informed consent within 28 days from study drug administration can be used as Screening 2 data if it meets the requirement of the protocol. If positive, perform when it is required to confirm CR as soon as possible or when clinically indicated.
- h: The data of bone marrow examination before informed consent within 42 days from study drug administration can be used as Screening 2 data if it meets the requirement of the protocol. If positive or indeterminate, perform when it is required to confirm CR as soon as possible or when clinically indicated.
- i: Subjects should not take study drug before evaluations are performed, unless specified (except tumor assessments and peripheral blood smear morphology assessment).
- j: On Day 15 of each cycle, peripheral blood smear morphology assessment can be omitted at the discretion of the investigator or subinvestigator, if there was no concern for safety of the subject.
- k: In Cycle 13 or later, visits and assessments on Day 15 can be omitted at the discretion of the investigator or subinvestigator, if there was no concern for safety of the subject.
- 1: Final observation is unnecessary for subjects who meet approved indication and receive commercial tazemetostat.

Eisai Confidential Page 53 of 71

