9.1.1.1 Pre-treatment Phase

The Pre-treatment Phase consists of Screening 1, Screening 2, registration, and baseline assessment. In Screening 1, the EZH2 gene mutation will be confirmed at central laboratory in patients with histologically diagnosed as FL (cohort 1) or DLBCL (cohort 2) who are available to provide archival tumor sample (Inclusion Criteria 1) and not apparent to conflict other eligible criteria to participate in the study. The archival tumor samples will be submitted to the central laboratory, and then this will be reported to the sponsor. If EZH2 gene mutation was confirmed, conduct Screening 2 to confirm the other eligibility for study treatment. Obtain the written informed consent with regards to tumor EZH2 gene mutation test and study treatment respectively, before Screening 1 and Screening 2. Screening 2 will last no longer than 28 days before the start of study treatment. After screening assessments, the patient who meets the inclusion criteria and does not meet the exclusion criteria will be enrolled. The baseline assessment will be conducted within 3 days before the treatment in order to confirm that the patient continues to meet the inclusion criteria and does not meet the exclusion criteria before moving to the Treatment Phase.

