- (16) Women of childbearing potential or man of impregnate potential who don't agree that both the patient and his/her partner will use a medically effective method for contraception (as the below note) for periods from before informed consent to during the clinical study and 30 days later (for males 90 days later) from last administration of study drug.
- (17) Woman who is pregnant or breastfeeding (not eligible even if she discontinues breastfeeding)
- (18) Patient who was decided as inappropriate for medical or other reasons to participate in the study by the investigator or sub-investigator
- (19) Patient who has a prior history of myeloid malignancy including T-cell lymphoblastic lymphoma, T-cell acute lymphoblastic leukemia or myelodysplastic syndrome

Note: Condom*, contraceptive sponge**, foam**, jelly**, diaphragm*, intrauterine device (IUD)*, or use of oral contraception* from at least 30 days before starting the study treatment (*Approved drugs or certified medical devices in Japan, **Non-approved drugs or certified medical devices in Japan)

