9.4.3 Method of Assigning Subjects to Treatment Groups

This is an open-label, single-arm study. All subjects who provide signed informed consent and satisfy all eligibility requirements (see Section 9.3) will receive study drug. There is no randomization in this study.

Screening 1

- (1) The investigator, subinvestigator, or clinical research coordinator will issue the Subject ID Number to individual subjects who provide signed informed consent for tumor EZH2 gene mutation test and record the date of informed consent for the test in "Subject Screening Log."
- (2) The archival tumor samples will be submitted to the central laboratory.
- (3) The sponsor will be notified by fax immediately after the archival tumor samples are submitted.
- (4) The result of the tumor EZH2 gene mutation test will be recorded in "Subject Screening Log."

Screening 2

The same Subject ID Number will be used for the same subject in Screening 1 and Screening 2, in principle.

(1) The investigator, subinvestigator, or clinical research coordinator will record the date of

Eisai Confidential Page 38 of 71 FINAL: 29 Jan 2021

- informed consent for study treatment in "Subject Screening Log" for the subjects who were confirmed to have EZH2 gene mutation and have signed the consent.
- (2) The investigator or subinvestigator will screen the subjects and determine subject eligibility based on the inclusion and exclusion criteria. The decision on the subject eligibility will be recorded in "Subject Screening Log."
- (3) The sponsor will be notified of date of informed consent for study treatment, date of screening initiation, expected treatment start date, and eligibility decision by fax immediately after the investigator or subinvestigator determines the subject eligibility (registration to study).
- (4) The investigator or subinvestigator will reconfirm the subject eligibility based on the results of baseline assessment according to the inclusion and exclusion criteria. The investigator or subinvestigator will record the subject eligibility in medical charts and initiate study drug administration.

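### The pregnancy test is scheduled only at Screening 2 and Discontinuation, so the exclusion of pregnant women can rest on a result up to 28 days old at first dose; one Baseline mark would bring this to 3 days.

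*Protocol*

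**What the plan says.** Protocol Table 5 (section 9.5.2.1) has a row "Pregnancy test (if applicable" with two marks, one under Screening 2 and one under Discontinuation. The Screening 2 column is headed as within 28 days before administration, and the Baseline column as within 3 days. Section 9.5.1.5.7.2 sets no timing of its own: "A serum or urine sample will be taken at visits as designated in the Schedule of Procedures/Assessments (Table 5". None of footnotes a to l adds a pregnancy test.

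Pregnancy is an eligibility matter under Exclusion 17 (section 9.3.2): "Woman who is pregnant or breastfeeding (not eligible even if she discontinues breastfeeding". Section 9.1.1.1 gives the order of events. First, "After screening assessments, the patient who meets the inclusion criteria and does not meet the exclusion criteria will be enrolled". Then, "The baseline assessment will be conducted within 3 days before the treatment in order to confirm that the patient continues to meet the inclusion criteria"; the same check covers the exclusion criteria. Section 9.4.3 (Screening 2, step 4) says the investigator or subinvestigator "will reconfirm the subject eligibility based on the results of baseline assessment according to the inclusion and exclusion criteria".

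Table 5 marks the inclusion/exclusion criteria again at Baseline. It also repeats body weight, physical examination, vital signs, ECOG performance status, ECG, hematology, chemistry and urinalysis there. Footnote a states: "Screening 2 assessments may be used as baseline assessments if performed within 3 days of the first administration of study drug".

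Once treatment has begun, pregnancy is discontinuation criterion (4) in section 9.3.3.1. Section 9.5.4.2 requires it to be reported within 1 business day of the investigator learning of it, and the subject to be withdrawn.

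**The concern.** The Baseline visit exists to show, close to the first dose, that the patient is still eligible. For criteria that can change over a few weeks, Table 5 mostly supplies fresh data: performance status for Inclusion 6, chemistry for Inclusions 8 and 9, hematology for Inclusion 10, and the ECG for Exclusion 9. Pregnancy can also begin between Screening 2 and first dose, and a urine test can look for it, yet Exclusion 17 gets no new result.

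A woman who conceives after her Screening 2 test could therefore start tazemetostat with no scheduled test to show it. Discontinuation, reporting and withdrawal all depend on the pregnancy becoming known. Under Table 5 the next scheduled test comes only when treatment ends, and treatment has no fixed length. What is at stake is fetal exposure and late withdrawal. No endpoint or analysis set is involved.

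**Working it through.** The plan states no figure for the age of the test result, so there is none to reproduce. The check is a reading of the schedule followed by simple date arithmetic.

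**1. Where the test falls.** Table 5 has nine visit columns. Six rows were split into those columns, and each gave nine cells, so the pregnancy row has not visibly shifted in extraction.

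| Row | Visits marked |
|---|---|
| Inclusion/exclusion criteria | Screening 2, Baseline |
| ECOG performance status | Screening 2, Baseline, Cycle 2+ Day 1, Discontinuation |
| 12-lead ECG | Screening 2, Baseline, C1D15, Cycle 2+ Day 1 and Day 15, Discontinuation |
| Hematology | Screening 2, Baseline, C1D15, Cycle 2+ Day 1 and Day 15, Discontinuation, Final observation |
| Virus test | Screening 2 |
| Pregnancy test | Screening 2, Discontinuation |

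**2. Maximum age of the result at first dose.** This equals the width of the window of the last scheduled pre-dose test.

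- As written: the Screening 2 window, 28 days.
- With a Baseline mark: the Baseline window, 3 days.
- Reduction: 28 − 3 = 25 days.

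These are maxima. A test done late in Screening 2 is already more recent, and under footnote a one done within 3 days of dosing would already count as the Baseline test.

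**3. Time on treatment without a scheduled test.** The Synopsis (Efficacy Assessments) describes central review of images obtained within 24 months after the last subject's enrollment, with a cut-off of 02 Dec 2020. Counting back 24 months puts last enrollment at about 02 Dec 2018. This is an inference; the date is not stated. The Protocol version is dated 29 Jan 2021 and a cycle is 28 days.

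- 02 Dec 2018 to 29 Jan 2021 = 789 days.
- If dosed on the enrollment date: 789 / 28 = 28.2 cycles.
- If dosed 28 days later: (789 − 28) / 28 = 761 / 28 = 27.2 cycles.

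So the last-enrolled patient, if still on treatment at this version, had passed about 27 to 28 cycles. Anyone enrolled earlier and still on treatment had passed more, so for a woman still on treatment this range is a minimum.

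**4. Feasibility of the change.** Urinalysis is marked at Baseline and on Day 1 of Cycle 2 and later, and section 9.5.1.5.7.2 accepts a urine sample. An added hCG test at those visits needs no new visit and no invasive procedure.

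**The case against.** The strongest reply is that no rule in the Protocol is broken and the main fix comes too late. Section 9.5.1.5.7.2 and Table 5 agree with each other. Sections 9.1.1.1 and 9.4.3 ask for eligibility to be reconfirmed, not for every screening test to be repeated. Virus tests, CT, PET and bone marrow are not repeated at Baseline either, and footnote h accepts marrow data up to 42 days old. All of that stands, which is why this is a gap in testing frequency and not a contradiction. Pregnancy still differs, because it can begin inside the window and is cheap to test for.

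Second, contraception already covers the window. Under Exclusion 16 patient and partner must agree that they "will use a medically effective method for contraception (as the below note) for periods from before informed consent to during the clinical study" and beyond it, and the note to that criterion asks for oral contraception, where used, to start at least 30 days before treatment, which is longer than the 28-day window. This lowers the risk considerably. But it is an agreement, and the accepted methods include condom, foam and jelly. The Protocol does not treat it as sufficient on its own, since it also tests at Screening 2. The gap matters only where contraception fails or is not followed.

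Third, enrollment appears to have ended before this version, so a Baseline mark protects nobody already enrolled. That stands. The SAP (section 5.6.2) plans an adverse-event table for follicular lymphoma subjects who continued after approval. This shows that continued treatment was foreseen, but not that any woman of childbearing potential was still being dosed. Subjects within the approved indication also move to commercial drug once it is available at their site. The present benefit of on-treatment testing is therefore possible but undocumented.

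Finally, nothing bars an unscheduled test, and a physical examination is done at Baseline. Neither provides a scheduled result.

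**Conclusion.** The concern holds as a modest safety point worth considering. Exclusion 17 can rest on a pregnancy result up to 28 days old at first dose, although the Protocol's own eligibility recheck falls within 3 days, and no routine test is scheduled on treatment. The reading of the table is certain.

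The practical size is small and rests on assumptions. Few women of childbearing potential are likely among the 8 + 13 = 21 planned efficacy-evaluable patients; the documents give no number, and it could be zero. The 27 to 28 cycles depend on the inferred last-enrollment date and on continuing treatment. The objective response rate, its confidence interval and the rest of the analysis do not change.

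**What to change.** Add an X for the pregnancy test in the Baseline column of Table 5, for women of childbearing potential; urine hCG is enough. Keep the Screening 2 mark, so that the test still precedes enrollment and sits alongside the screening CT and PET. Footnote a already avoids a duplicate when Screening 2 falls within 3 days of dosing.

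Optionally, for women still on treatment, add a mark on Day 1 of Cycle 2 and later. The interval is a clinical choice for the sponsor. With enrollment apparently closed, this is the only part that could help a current patient; the Baseline mark is for any later protocol that reuses the schedule.

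The cost is one cell in Table 5 and one extra urine hCG for a few women. The optional mark is a second cell and one urine hCG per 28-day cycle for the same few women.

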9.1.1.3 Follow-up Phase

Follow-up Phase consists of the evaluation at discontinuation which is performed within 7 days after the discontinuation of the study and a final observation which occurs 30 days (+7 days) after final administration of tazemetostat or initiation of a new anti-tumor therapy, whichever occurs early. Final observation is unnecessary for subjects who withdraw from the study and continuously take commercial tazemetostat.

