9.5.1.3 Efficacy Assessments

Efficacy assessment will be performed by investigator or subinvestigator based on "Revised response criteria for malignant lymphoma (IWG-2007)" (Cheson, et al., 2007). Overall response and best overall response (BOR) (best response recorded at the designated visits during the study) will be assessed. Perform the assessment below for tumor assessment.

CT scans will be performed at Screening 2, every 8 weeks from study drug administration up to first 32 weeks, then every 12 weeks and at discontinuation.

Eisai Confidential Page 42 of 71 FINAL: 29 Jan 2021

PET scans will be performed at Screening 2. If positive, perform when it is required to confirm CR as soon as possible or when clinically indicated.

If gastrointestinal disease is suspected, endoscopic examination will be performed at Screening 2. If exists, perform when it is required to confirm CR as soon as possible or when clinically indicated.

To evaluate bone marrow infiltration, a bone marrow aspiration or biopsy will be performed at Screening 2. If positive or indeterminate, perform when it is required to confirm CR as soon as possible or when clinically indicated.

Also, central review will be conducted by the Imaging Review Committee for CT and PET assessment. In addition, Efficacy and Safety Evaluation Committee (ESEC) will conduct central evaluation based on the review of Imaging Review Committee and other assessment / bone marrow infiltration evaluated by the investigator or subinvestigator, to determine the overall responses and the best overall response.

The primary endpoint and the secondary endpoint with regard to efficacy are defined as below, and will be evaluated by the result of ESEC review.

ORR:

The rate of subjects whose BOR is CR or PR.

PFS

Defined as the term between the date of administration of the first dose of the study drug and the date of the first event (PD or death whichever occurs first). The detail of the censoring rule for PFS will be described in the statistical analysis plan (SAP).

• DOR:

Defined as the term between the date of confirmation of the first response and the date of confirmation of the PD. The detail of the censoring rule for DOR will be described in the SAP.

TTR·

Defined as the term between the date of administration of the first dose of the study drug and the date of confirmation of the first response.

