### 5.4.2 Secondary Efficacy Analyses

- Analysis of PFS

PFS will be summarized by Kaplan-Meier method using median with 95%CI. Kaplan-Meier curve will be provided. The number of event/censor (percentage) and reasons of censor will be also summarized.

- Analysis of DOR

DOR will be summarized by Kaplan-Meier method using median with 95% CI in responders. The number of event/censor (percentage) and reasons of censor will be also summarized.

- Analysis of TTR

TTR will be summarized using descriptive statistics in responders.

PFS will be calculated as:

End date for PFS – Date of administration of the first dose of study drug + 1 (day)

DOOR will be calculated as:

End date for DOOR – Date of the first response + 1 (day)

End date of PFS and DOOR is defined as the table below:

Situation	End Date for PFS and DOOR	Censored
Documented progression disease (PD) during the study	Date of the first assessment of the series of the tests that determined PD	No
Death during the study before PD	Date of death	No
No baseline assessments	Date of administration of the first dose of study drug	Yes
Treatment discontinuation without post-baseline tumor assessments	Date of administration of the first dose of study drug	Yes
Treatment discontinuation without documented PD or death with post-baseline tumor assessments	Date of last tumor assessment before discontinuation	Yes
New anticancer treatment started prior to disease progression	Date of last tumor assessment before start of new treatment	Yes
Death or PD after more than one missed tumor assessments	Date of the last tumor assessment before missed assessments	Yes
Subjects still on treatment without PD as of data cut-off	Date of last tumor assessment	Yes

TTR will be calculated as:

Date of first response – Date of administration of the first dose of study drug + 1 (day)

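### A CT from the previous 28 days may replace the discontinuation CT even if it shows no progression, so some progressions that prompt stopping may be censored in committee-assessed PFS and DOR; add a sensitivity analysis.

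*Protocol*

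**What the plan says.** CT is scheduled "every 8 weeks from study drug administration up to first 32 weeks, then every 12 weeks and at discontinuation" (Protocol 9.5.1.3). Footnote f to Table 5 allows one week either side of each scheduled scan and adds: "The data within 28 days can be used as discontinuation data". It does not say what the 28 days are counted from, that the reused scan must be post-baseline, or that it must show progressive disease (PD).

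Table 5 marks CT at discontinuation and not at final observation. Protocol 9.1.1.3 describes nothing later: "Follow-up Phase consists of the evaluation at discontinuation which is performed within 7 days after the discontinuation of the study and a final observation". Stopping for progression rests on the site's own evaluation (Protocol 9.1.1.2). The primary and secondary efficacy endpoints, by contrast, "will be evaluated by the result of ESEC review" (Protocol 9.5.1.3).

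The end-date table in SAP 5.4.2 counts documented PD, and death before PD, as events. A subject who stops treatment with neither is censored at the last tumour assessment before stopping. A further row, "New anticancer treatment started prior to disease progression", censors at the last assessment before the new treatment. SAP 5.4 also reports investigator-assessed results. SAP 5.4.3 lists no other efficacy analyses, and no sensitivity analysis of PFS or DOR is planned.

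**The concern.** Take a subject who is stable on the Week 8 CT, deteriorates, and is taken off treatment at Week 11 because the site judges that the disease has progressed. The Week 8 scan is 21 days old, so it can serve as the discontinuation CT. ESEC then has no newly scheduled image, and unless it calls PD on other grounds the subject is censored at Week 8.

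This censoring is informative. The subject leaves the risk set because of the very event being estimated, and Kaplan-Meier treats the subject as having the same future as those still stable. PFS and DOR by ESEC would be too high. The cohorts are planned at 8 and 13 evaluable subjects, so one reclassified event moves the curve visibly.

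**Working it through.** **What the plan gives.** The documents state no PFS or DOR assumption, so there is no plan figure to reproduce. The sample sizes of 8 and 13 rest on ORR alone and do not depend on this point.

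**How often the waiver is available.** If stop times are spread evenly over a scan interval, the share with a CT in the last 28 days is 28 divided by the interval.
- 8-weekly phase: 28/56 = 50%. With one week either side of each scan the interval is 42 to 70 days, giving 67% to 40%.
- 12-weekly phase: 28/84 = 33%. With an interval of 70 to 98 days, 40% to 29%.

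**Model for the bias (assumptions, not in the documents).** Time to progression is exponential with median *m* weeks, so S(t) = 2^(−t/m). A fraction *q* of progressions is clinical and prompts stopping at once; the rest are found at the next CT. Without the waiver a clinical progressor is scanned and counted. With it, a clinical progressor within 4 weeks after a post-baseline CT is censored at that CT. Full use of the waiver is assumed first. Then

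- KM(8) = S(8)
- KM(16) = KM(8) × S(16) / [S(8) − q{S(8) − S(12)}]
- KM(24) = KM(16) × S(24) / [S(16) − q{S(16) − S(20)}]

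**Worked case, m = 16, q = 0.25.** S(8), S(12), S(16), S(20), S(24) = 0.7071, 0.5946, 0.5000, 0.4204, 0.3536.
- KM(16) = 0.7071 × 0.5 / (0.7071 − 0.25 × 0.1125) = 0.3536 / 0.6790 = 0.5207
- KM(24) = 0.5207 × 0.3536 / (0.5 − 0.25 × 0.0796) = 0.5207 × 0.3536 / 0.4801 = 0.383

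The true value is 0.354, so the shift is 3.0 points. If only half of eligible subjects use the waiver, q becomes 0.125, KM(24) is 0.368 and the shift is about 1.4 points.

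**24-week PFS, waiver always used:**

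| Median (weeks) | No waiver | q = 10% | q = 25% | q = 50% |
|---|---|---|---|---|
| 12 | 0.250 | 0.261 | 0.278 | 0.311 |
| 16 | 0.354 | 0.365 | 0.383 | 0.417 |
| 24 | 0.500 | 0.511 | 0.528 | 0.559 |
| 32 | 0.595 | 0.605 | 0.620 | 0.647 |

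**Subjects affected.** The share of clinical progressors censored is the sum of S(c) − S(c+4) over the post-baseline CT weeks c = 8, 16, 24, 32, 44, and so on. It is 33% to 36% across these medians. At m = 16 and q = 25% it is 34.6%: 13 × 0.25 × 0.346 = 1.1 subjects in cohort 2 and 8 × 0.25 × 0.346 = 0.7 in cohort 1.

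**If stopping is unrelated to progression** (toxicity, for example). With median PFS of 3 months the daily hazard is ln 2 / (3 × 30.44) = 0.00759. The chance of PD since a reused CT, averaged over 0 to 28 days, is 9.9%. Even if every subject stopped this way in the 8-weekly phase, the expected loss is 8 × 0.5 × 0.099 = 0.40 or 13 × 0.5 × 0.099 = 0.64 events, and less with longer medians. The bias matters only when deterioration prompts the stop.

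**The case against.** The best reply is that little of this reaches a conclusion. PFS and DOR are secondary, carry no threshold, and SAP 5.3.3 plans no comparison. An approximate 95% interval for 24-week PFS near 0.354 is ±1.96√(0.354 × 0.646/n): about ±26 points for n = 13 and ±33 for n = 8. A 3-point shift is small beside that. Investigator-assessed results are reported too, and SAP 5.4.2 already tabulates reasons for censoring. All of this stands and limits the weight of the point. It does not remove the bias, which runs in one direction, and none of the planned outputs shows its size in the ESEC curve.

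Four stronger readings are tempting and are not supported.

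- *All progression at stopping is censored.* It is not. If the reused CT shows PD, as when a scheduled scan prompts the stop, or a fresh discontinuation CT shows it before new therapy, SAP 5.4.2 counts an event. Death before PD also counts.
- *ESEC cannot call PD without a new CT.* ESEC also uses other site assessments and bone marrow findings, and PET is allowed when clinically indicated if positive at screening. The detailed response criteria are in an attachment that is not among these documents. Hence such a subject may be censored, not must be.
- *New therapy routinely starts before the discontinuation CT, so its PD is lost.* Footnote b says "final observation must be conducted before initiation of other anti-tumor therapy", and the discontinuation evaluation comes before the final observation in the visit order. That largely closes the route. Protocol 9.4.7.1, which moves a subject to follow-up once anti-tumour therapy is given, is loosely worded, and no sentence orders the CT explicitly. That calls for clarification and does not show a loss of events.
- *The DLBCL cohort is hit hardest.* The documents give no rate of clinical progression between scans for either cohort.

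**Conclusion.** The point holds in a limited form. Footnote f, the absence of a later scheduled CT, stopping on site evaluation and the censoring rule in SAP 5.4.2 together allow informative censoring that biases ESEC PFS and DOR upward.

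The size is at most about 1, 3 or 5 to 6.5 points on 24-week PFS for 10%, 25% or 50% clinical progressions, and about half that at 50% use of the waiver. These are upper figures: they assume exponential progression with medians of 12 to 32 weeks, full use of the waiver, and that ESEC never calls PD on other evidence. DOR was not modelled separately; the direction is the same because SAP 5.4.2 uses one end-date table for both. ORR is untouched by this mechanism, since progression after an earlier scan does not alter a best response already recorded.

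**What to change.** Add to SAP 5.4.2 a sensitivity analysis of ESEC PFS and DOR in which discontinuation for site-evaluated progression, or the start of new anti-tumour therapy, is an event on that date. The primary reason for discontinuation is on the CRF (Protocol 9.5.5), therapies are recorded up to the final observation (Protocol 9.4.7), and the SAP's own new-treatment row already needs the therapy date. This assumes that the CRF reason separates progression from other reasons.

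The cost is one extra table. Counting new therapy as an event can bias the estimate downward, so this should remain a sensitivity analysis beside the main one. If results have already been seen, label it exploratory as SAP 5.7 requires.

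For imaging still to be collected, reconcile footnotes f and b. State what the 28 days are counted from, that a reused CT must be post-baseline (as written, a subject who stops very early could reuse the Screening 2 scan), and how the discontinuation tumour assessment is ordered relative to new anti-tumour therapy. This is wording only. It cannot change the central review, whose imaging cut-off of 02 Dec 2020 (Protocol Synopsis) precedes the current protocol of 29 Jan 2021, so the SAP change is the one that matters.

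A repeat CT for every subject who stops is not proposed. It would rescan subjects who stop for toxicity soon after a stable scan, for little gain.
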